4.3 Duration of Therapy

In the absence of treatment delays due to AE(s), treatment may continue for a maximum of 12 cycles or until one of the following criteria listed in [Section 4.5](#) applies. If CR is achieved, the participant will receive one cycle beyond CR. Treatment may be resumed if KS progresses off treatment after a CR, up to a maximum of 12 cycles. The participant will resume the previous dose that he/she was receiving when CR was achieved. Participants who achieve PR or SD may continue the treatment at the dose he/she was receiving when PR or SD was achieved for a maximum of 12 cycles, if the participant and treating physician feel that it is beneficial to continue treatment.

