4.4 Duration of Follow-up

Participants who have PR or better will be followed up every three months, for up to one year, or until an earlier time of disease progression requiring additional treatment. All other participants will be followed for 4 weeks after completion of study treatment, removal from study treatment, or until death, whichever occurs first. Participants who do not achieve a PR or better and are removed from treatment early will be reported as off-treatment on the last date of agent administration. Participants removed from study treatment for unacceptable AE(s) will be followed until resolution or stabilization of the AE. Participants who withdraw from treatment for toxicity reasons should be followed until the toxicity resolves/returns to baseline, or for 4 weeks, whichever is later. In addition, participants who go off study treatment for reasons other than toxicity should be followed for at least 4 weeks after discontinuing drug.

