4.5 Criteria for Removal from Treatment

Participants will be removed from study treatment when any of the criteria listed in [Section 5.0](#) and below applies. The reason for study treatment removal and the date of the participant's last treatment must be documented in the Off Protocol Treatment Form in Advantage eClinical. The date the participant was removed from study treatment must be documented in the source.

- Uncontrolled sustained hypertension, which will be defined as systolic BP > 140, and diastolic BP > 90, even with use of antihypertensive medications.
- Disease progression after completing 2 or more cycles (or at least after 4 doses of sEphB4-HSA).
- Dose delay of more than 28 days.
- Rapid progression of disease that is deemed to be life-threatening.
- Intercurrent illness that prevents further administration of treatment.
- Any participant who develops Multicentric Castleman's disease or a life-threatening systemic inflammatory syndrome will not receive further sEphB4-HSA and will be managed using the best judgment of the treating physician.
 - **These events require mandatory notification of a study chair within 24 hours which will result in immediate notification of all participating sites and a conference call to assess the safety of continued enrollment.**
- Participants who experience Steven-Johnson Syndrome or major allergic reaction.
- Participants who become pregnant or need to breast-feed.
- Participants who require systemic chemotherapy for the treatment of a malignancy other than KS.
- Participants who are noncompliant with respect to taking drugs, keeping appointments, or having tests required for the evaluation of drug safety and efficacy.
- Participants have the right to withdraw from the study at any time for any reason.

- The Investigator has the right to remove participants from the study for clinical reasons which he/she believes are life-threatening to the participant even if such reasons do not fall into the toxicity classifications discussed in [Section 5.0](#).
- General or specific changes in the participant's condition render the participant unacceptable for further treatment in the judgment of the investigator.
- Unacceptable AE(s).

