8.4 Post-treatment Evaluation

All participants must be seen 4-6 weeks after discontinuation or completion of study treatment (counting from Day 28 of the final cycle). If participants are unable to return to the clinic, attempts should be made to obtain follow-up information from the treating physician regarding performance status, tumor status, toxicity, and subsequent care. Participants who withdraw for toxicity reasons should be followed until the toxicity resolves/returns to baseline, or for at least 4 weeks, whichever is later. In addition, participants who go off treatment for reasons other than toxicity should be followed for at least 4 weeks after discontinuing drug.

The following procedures should be performed during the post-treatment evaluation visit:

- CBC with differential.
- Serum chemistries: liver enzymes (AST [SGOT], ALT [SGPT]), alkaline phosphatase, BUN, creatinine, electrolytes (sodium, potassium, chloride, bicarbonate, calcium, phosphorus, glucose), total protein, albumin, bilirubin (direct and indirect).
- Complete physical examination including: vital signs, weight, ECOG or KPS performance status, signs and symptoms review, and toxicity evaluation (AEs must be reported per [Section 6.4](#)).
- Review of AIDS-defining events.
- KS tumor assessment with photographic records if there are any changes from the treatment discontinuation visit. Response of KS to treatment with sEphB4-HSA will be assessed as described in [Section 9.1](#).

- KS staging ([Appendix VII](#)).
- If the participant had documentation of visceral disease while on study, documented re-evaluation of visceral disease.
- FAHI+KS quality of life questionnaire ([Appendix XII](#)). Those who have HIV-negative KS will not have the HIV portion scored.
- At a participant's final study visit the Off-Study Summary Form will be completed.

Telehealth follow-up visits are permitted in the event an in-person visit is restricted and a response evaluation is not required at that visit. The complete physical examination will be deferred (i.e., vital signs, physical); however, symptoms review, and AIDS-defining events review will be conducted via teleconference. If there is any concern of progression or symptoms related to progression of KS, an in-person visit is required to follow the telemedicine visit within 2 weeks.

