9.0 MEASUREMENT OF EFFECT

All participants will be evaluated for response by physical examination on Day 1 of every cycle (± 3 days). See [Appendix I](#) for the KS Tumor Assessment schedule.

CTEP-registered physician investigators and CTEP-registered advanced practice clinicians who are non-physician investigators (i.e., NP or PA) may perform toxicity and response assessment per local licensure requirements.

Evaluable for toxicity:

All participants will be evaluable for toxicity from the time of their first treatment with sEphB4-HSA. For the primary toxicity endpoint, we will report toxicities occurring during the first two cycles of therapy.

Evaluable for objective response:

Only those participants who have measurable disease present at baseline, have received at least two cycles of therapy, and have had their disease re-evaluated will be considered evaluable for response. These participants will have their response classified according to the definitions stated below (Note: Participants who exhibit objective disease progression prior to the end of Cycle 1 will also be considered evaluable.). For the primary efficacy endpoint, we will report the clinical response (CR or PR) rate after 2 or more cycles of treatment. Participants with KS which progress prior to the end of Cycle 2 will be considered to have treatment failure.

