The observed proportions of participants experiencing clinical response and unacceptable toxicity will be calculated, as well as 95% confidence intervals. This will be done for the primary endpoint related to clinical response and unacceptable toxicity after a minimum of 2 cycles of therapy at the 10 mg/kg every two weeks dose level, and separately for response and toxicity at later cycles. Participants treated prior to version 4 dosed at 15 mg/kg every two weeks (n=3) will be combined with those treated at the revised dose level in analyses; a sensitivity analysis excluding these participants will also be performed to investigate the

impact of these participants on the primary outcomes. Adverse events will be tabulated according to type and severity. The Kaplan-Meier method will then be used to estimate the distribution of time to response, time to relapse, and time to death. Time to response is defined as time from the first dose of treatment until documentation of first response. Time to progression is defined as time from initiation of chemotherapy to documentation of first progression. Response duration is defined as the time from first documentation of response to documentation of first progression.

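### Kaplan-Meier is named for time to response and time to death with no competing-event rule and with follow-up that depends on response, so both descriptive curves may be too favourable

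*Combined protocol and SAP*

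**What the plan says.** The primary endpoint analysis plan in Section 10.1 names one method for three time-to-event quantities: "The Kaplan-Meier method will then be used to estimate the distribution of time to response, time to relapse, and time to death". For response it adds: "Time to response is defined as time from the first dose of treatment until documentation of first response". It does not say what happens to a participant who progresses, dies or stops before responding. Time to death is not defined.

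Follow-up differs by outcome. For responders, Section 4.4 says: "Participants who have PR or better will be followed up every three months, for up to one year", with an earlier end at progression that needs further treatment; Section 8.5 counts this period from Day 28 of the final cycle. For non-responders, Section 4.4 says: "All other participants will be followed for 4 weeks after completion of study treatment, removal from study treatment, or until death, whichever occurs first". Section 8.4 sets one closing visit for everyone: "All participants must be seen 4-6 weeks after discontinuation or completion of study treatment (counting from Day 28 of the final cycle").

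Treatment length varies. Section 4.3 says "treatment may continue for a maximum of 12 cycles", and this includes participants with stable disease. Section 4.5 lists among the reasons for removal: "Disease progression after completing 2 or more cycles (or at least after 4 doses of sEphB4-HSA"). Section 9.0 adds, for the efficacy endpoint: "Participants with KS which progress prior to the end of Cycle 2 will be considered to have treatment failure". Section 10.7 counts progression, early death and unknown status as treatment failure in the main response analysis.

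**The concern.** For response, Kaplan-Meier treats a censored participant as someone who would have gone on to respond at the same rate as those still under observation. A participant taken off treatment for progression, or who has died, is not in that position, and Sections 9.0 and 10.7 count such participants as failures. If they are censored at that event, the curve estimates response in a population where nobody progresses or dies first. Its plateau then lies above the response proportion given in the same paragraph of the plan, and one report carries two conflicting response figures.

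For death, how long a participant is watched depends on whether they responded. Non-responders leave the risk set within weeks of stopping treatment, while responders can stay for a further year. If response and mortality are related, censoring is informative and the later part of the curve is drawn from the better-prognosis group. Responders' follow-up also ends at progression requiring treatment, so their later deaths can be missed. Section 6.4.2 does not fill the gap: it asks only for drug-related deaths that a site happens to learn of.

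**Working it through.** **The plan's own figures.** The documents give no figure for these curves. The design figures in Section 10.2 reproduce by exact binomial, with response and toxicity taken as independent:
- Power = P(X ≥ 9 | 20, 0.6) × P(Y ≤ 3 | 20, 0.1) = 0.9435 × 0.8670 = 0.818 (stated 0.82).
- Alpha = max{P(X ≥ 9 | 20, 0.3), P(Y ≤ 3 | 20, 0.3)} = max{0.1133, 0.1071} = 0.1133 (stated 0.11).

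Neither uses a time-to-event curve.

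**Observation windows** (Sections 4.3, 4.4, 4.5, 8.4 and 8.5, ignoring dose delays):
- Non-responder removed after 2 cycles: 8 weeks of treatment, last seen at week 8 + 4 = 12 to 8 + 6 = 14.
- Non-responder treated for all 12 cycles: 48 weeks of treatment, last seen at week 48 + 4 = 52 to 48 + 6 = 54.
- Responder treated for all 12 cycles: up to week 48 + 52 = 100, or earlier at progression requiring treatment.

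So after about week 52-54 only responders remain at risk, by design.

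**Time to response.** The documents give no progression rates, so these are assumptions. Let F be the true proportion responding by cycle 12 and G the proportion progressing or dying first, with constant cause-specific hazards. Censoring at progression or death gives 1 − KM = 1 − (1 − F − G)^(F/(F+G)).

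| F (true) | G | 1 − KM | Excess |
|---|---|---|---|
| 0.30 | 0.20 | 0.340 | 0.04 |
| 0.30 | 0.40 | 0.403 | 0.10 |
| 0.30 | 0.60 | 0.536 | 0.24 |
| 0.45 | 0.20 | 0.517 | 0.07 |
| 0.45 | 0.40 | 0.634 | 0.18 |
| 0.60 | 0.10 | 0.644 | 0.04 |
| 0.60 | 0.20 | 0.701 | 0.10 |
| 0.60 | 0.35 | 0.849 | 0.25 |

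F = 0.30 and F = 0.60 are the null and alternative response rates of Section 10.2. A per-cycle version agrees. With 8% responding and 12% leaving in each of cycles 2-12, 1 − KM = 1 − 0.92^11 = 0.600, against a true 0.4 × (1 − 0.8^11) = 0.366. With 5% and 10%, it is 1 − 0.95^11 = 0.431 against (1/3) × (1 − 0.85^11) = 0.278.

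If progressors and deaths are instead kept in the risk set to the end of the window as never responding, the curve equals the cumulative incidence F and the excess is zero.

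**Time to death.** The documents give no death rates, so these are again assumptions. The simulation had 400,000 participants per scenario and 30% or 60% responders. Time on treatment was at least 8 weeks and capped at 48, with a mean before the cap of 20 weeks for non-responders and 38 for responders. Non-responders were censored 4 weeks after treatment and responders 52 weeks after. Responder follow-up was not cut at progression.

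| Annual death hazard, non-responder / responder | KM minus true survival, week 52 | Week 78 |
|---|---|---|
| 0.05 / 0.05 | 0 | 0 |
| 0.10 / 0.05 | 0.01 | 0.02-0.03 |
| 0.20 / 0.05 | 0.03-0.04 | 0.05-0.08 |
| 0.20 / 0.02 | 0.03-0.04 | 0.06-0.09 |
| 0.40 / 0.05 | 0.05-0.08 | 0.09-0.15 |

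Ranges run over the two responder proportions.

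**The case against.** The strongest reply is that the plan never says progressors are censored. It is silent, and one permissible reading, in which they stay at risk as never responding, has no bias. That stands: the response bias is conditional. But the plan names Kaplan-Meier and writes no rule, so ordinary censoring at progression or last assessment is a likely default.

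Several stronger readings are tempting, and the documents do not support them.
- A reader might infer that anyone who progresses or stops treatment can no longer respond. Sections 8.3 and 8.4 still require a response assessment at discontinuation and 4-6 weeks later, and progression before 4 doses does not by itself require removal. A participant who stops with stable disease is a non-responder but is not labelled a treatment failure in Section 10.7.
- A reader might infer that non-responders are followed for only 4 weeks in all. The 4 weeks run from the end of treatment, and stable disease can be treated for 12 cycles. For roughly the first year the survival curve therefore does not describe responders alone.
- A reader might infer that the survival bias must be large. It depends on the hazards and on how long non-responders stay on treatment. Take 40% responders treated for 6-12 cycles and annual hazards of 0.30 against 0.05. If all non-responders stop at 2-6 cycles, one-year Kaplan-Meier survival is 0.89 against a true 0.83. If half of them have stable disease treated for 12 cycles, it is 0.85 against 0.83. Section 3.2 also excludes patients who need front-line cytotoxic therapy, so a wide mortality gap cannot be taken for granted.
- A reader might infer that responders at least have equal follow-up among themselves. They do not: treatment length varies and follow-up stops at progression requiring treatment.

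It is also fair to say that the stakes are limited. Neither endpoint is named in the objectives, no decision rests on these curves, and with 20 participants sampling error will exceed most plausible survival biases.

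**Conclusion.** The point holds as a conditional one. Kaplan-Meier is specified for two endpoints whose censoring would be tied to prognosis, with no rule to prevent the resulting bias. With usual censoring, the response curve lies above the response proportion, by 0.04 to 0.25 in the scenarios run. The survival curve is supported only by responders after about week 52-54. If non-responders die faster, it is too high by about 0.01-0.08 at 52 weeks and 0.02-0.15 at 78 weeks. Both biases can be zero: for response if progressors and deaths are retained as never responding, for survival if mortality does not differ by response. All rates behind these sizes are assumed.

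It would be wrong to conclude that both curves will certainly favour the drug, or that the efficacy conclusion is compromised. The primary response proportion, the rule of at least 9 responders and at most 3 unacceptable toxicities in 20, the power and alpha do not change. The change is still worth making, because it removes an avoidable contradiction within one report at little cost.

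**What to change.** **Time to response.** Replace Kaplan-Meier with the cumulative incidence of response. The competing event should be progression, death, or the end of response assessment without response. Treatment discontinuation should not itself be the competing event, because a first response can still be documented at the discontinuation and 4-6 week visits. Use the same population and time window as the response rate, so that the plateau equals the reported proportion.

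**Time to death.** Define it. Then either report on-study deaths as a count, or limit the curve to the follow-up common to all participants. That window may be short, since a non-responder removed after two cycles is last seen at about week 12-14, so the count is the simpler choice. If a longer survival curve is wanted, record vital status for every participant on one schedule, whatever their response and including after progression.

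**Response duration and relapse.** State the censoring rule, and do not assume that responders have equal follow-up.

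**Cost.** A wording amendment to the statistical section, which under Section 12.2 needs CTEP and IRB approval, and a little more analysis work. The optional vital-status check adds one call or chart look-up per participant per time point.

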10.2 Sample Size/Accrual Rate

A total of 20 evaluable participants will be enrolled. The design was developed by considering the joint probability of clinical response and toxicity simultaneously (Jin H. Alternative designs of phase II trials considering response and toxicity, *Contemp Clin Trials* 28 (2007): 525-53). The null hypothesis for defining the unacceptable region based on clinical response rate and toxicity rate simultaneously and the alternative hypothesis for defining the region for a promising agent are as follows:

- $H_0: P_{\text{resp}} \leq 0.30 \text{ OR } P_{\text{tox}} \geq 0.30$
- $H_1: P_{\text{resp}} \geq 0.60 \text{ AND } P_{\text{tox}} \leq 0.10$

In a single stage design, 20 participants will be evaluated for clinical response and toxicity. Toxicity will be defined as: unacceptable toxicities as defined in [Section 10.1](#). All unacceptable toxicities that are possibly, probably, or definitely attributed to protocol therapy will be counted as a toxicity.

The null hypothesis will be rejected if there are at least 9 responders, and no more than 3 participants who experience unacceptable toxicities. This design has power of 0.82 and a significance level of 0.11. The planned accrual rate will be one participant per month.

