3.3 Number of Participants to be Enrolled

3.3.1 Proposed sample size

This study will enroll a minimum of 6 participants and a maximum of 20 participants.

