For phase I dose escalation trials, dose escalation (or dose de-escalation) is based on the rules in the protocol and the protocol chair, AMC medical monitor, and protocol statistician determine whether these criteria have been met based on a review of all safety data for the protocol-defined evaluation period. If applicable for phase II trials, stopping the trial for toxicity or efficacy, or suspending enrollment pending observation of responses in a multi-stage phase II trial, is based on meeting criteria stated in the protocol, and the protocol chair, AMC medical monitor, and protocol statistician determine whether these criteria have been met.

Plans for Assuring Compliance with Requirements Regarding AE Reporting

The protocol chair, AMC group chair, and the AMC ODMC share responsibility in assuring that participating investigators comply with applicable regulatory and protocol requirements for AE reporting. The AMC site principal investigator certifies compliance with NCI and FDA requirements for trial conduct by signing the site subaward agreement for the grant and the AMC Adherence Statement for site membership; clinical investigators also certify compliance in completing the protocol signature page for each protocol active at the site, and Form FDA-1572 for CTEP investigator registration, and also for AMC IND studies sponsored by AMC investigators or industry sponsors. Protocol compliance with AE identification, assessment and reporting requirements is assessed by the AMC ODMC using several methods: 1) programmed system checks and messages to instruct the site to complete routine and/or expedited reporting when certain criteria are reported in the clinical data entry system; 2) programmed data reports provided to the protocol chairs that identify reports requiring expedited AE reporting; 3) remote review of data entry or data reports to ensure compliance with protocol and NCI AE reporting requirements; 4) AMC medical monitor review described in the section above; and, 5) routine site audits by reviewing the site's source documentation.

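### The protocol has no toxicity-count stopping rule, so accrual may continue after a fourth unacceptable toxicity, when the primary test can no longer reject H0

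*Combined protocol and SAP*

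**What the plan says.** Section 10.2 describes a single look: "In a single stage design, 20 participants will be evaluated for clinical response and toxicity". The decision rule is: "The null hypothesis will be rejected if there are at least 9 responders, and no more than 3 participants who experience unacceptable toxicities". The null is a response rate of 0.30 or less, or a toxicity rate of 0.30 or more. The alternative is a response rate of at least 0.60 with a toxicity rate of at most 0.10. The operating characteristics are given as: "This design has power of 0.82 and a significance level of 0.11". On timing: "The planned accrual rate will be one participant per month".

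Section 3.3.1 states the size differently: "This study will enroll a minimum of 6 participants and a maximum of 20 participants".

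Section 10 contains no interim look, curtailment or toxicity-count rule. Appendix XIII (Cohort trial reviews not subject to DSMB review) says that an early stop of a phase II trial, where applicable, "is based on meeting criteria stated in the protocol". It names the protocol chair, medical monitor and protocol statistician as those who judge whether the criteria are met.

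Sections 4.1 and 5.1 hold accrual after a major bleed or an unexpected event of grade 4 or higher. Section 9.0 limits the primary toxicity endpoint to the first two cycles.

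**The concern.** Once four participants have an unacceptable toxicity counted in the primary endpoint, the condition of no more than three has failed and no number of responders can rescue the test. Appendix XIII sends the reader to the protocol for a stopping criterion, and the protocol has no criterion based on a count. Further participants may then be exposed to a drug that has already failed the toxicity limit, in a trial whose primary decision is known. The minimum of 6 in Section 3.3.1 hints at some way of ending below 20, but no rule provides one.

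The existing hold does not fill the gap. It responds to single events, keeps no count, and leaves resumption to judgement. Section 6.2.6 treats an event as unexpected only if it is not listed in available sources, including the protocol. Hypertension is in Table 6-A; allergic reaction and decreased platelet count are in Table 6-C. Severe forms of these can be unacceptable toxicities under Section 10.1 without being unexpected. Prolonged grade 3 neuropathy also qualifies under Section 10.1 but is below grade 4.

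**Working it through.** **Inputs (Sections 9.0 and 10.2).** n = 20; success if responders X ≥ 9 and toxicities T ≤ 3; null rates 0.30 and 0.30; alternative rates 0.60 and 0.10; accrual of one per month; toxicity window of two 28-day cycles, or 8 weeks.

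**1. Reproduce the plan's figures.** These are exact binomial calculations, with response and toxicity taken as independent for power.

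- Power = P(X ≥ 9 | 20, 0.60) × P(T ≤ 3 | 20, 0.10) = 0.9435 × 0.8670 = 0.818, against 0.82 stated. Over every possible dependence between the two endpoints it lies between 0.811 and 0.867.
- Level = the larger of two boundary cases. With toxicity near 0, P(X ≥ 9 | 20, 0.30) = 0.1133. With response near 1, P(T ≤ 3 | 20, 0.30) = 0.1071. Both round to the stated 0.11.

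**2. Effect of closing at the fourth toxicity on the test.** Every path that reaches T = 4 already fails T ≤ 3. Stopping there turns no rejection into a non-rejection, or the reverse. Level and power stay at 0.1133 and 0.818, provided that the events counted for stopping are exactly those counted in the test.

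**3. Effect on enrolment.** Let M be the participant at whom the fourth toxicity occurs, and p the true rate.

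P(M = m) = C(m−1, 3) p⁴ (1−p)^(m−4), m = 4, …, 20

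E[N] = 20 − Σ P(M = m) × max(0, 20 − m − L)

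Here L is the number of participants who enter before the fourth event is known. The documents give no L. L = 2 is an assumption drawn from an 8-week window at one participant per month; L = 0 is instant reporting.

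| p | Fourth event within 20 | Fourth event before the 20th | E[N], L = 0 | E[N], L = 2 |
|---|---|---|---|---|
| 0.05 | 0.016 | 0.013 | 19.94 | 19.97 |
| 0.10 | 0.133 | 0.115 | 19.43 | 19.64 |
| 0.15 | 0.352 | 0.316 | 18.22 | 18.82 |
| 0.20 | 0.589 | 0.545 | 16.51 | 17.55 |
| 0.30 | 0.893 | 0.867 | 12.83 | 14.53 |
| 0.40 | 0.984 | 0.977 | 9.95 | 11.89 |

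At p = 0.30 the mean number spared is 20 − 12.83 = 7.2, or 20 − 14.53 = 5.5 with the lag. With L = 3, E[N] at p = 0.30 is 15.33. At the acceptable rate of 0.10 the mean spared is 0.6 (0.4 with L = 2).

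**4. Is the count defined?** Not yet.

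- Attribution: Section 10.1 counts events at least probably due to the drug, whereas Section 10.2 also counts possibly related ones.
- Window: Section 9.0 uses the first two cycles, but treatment may run to 12. A rule without a window could close accrual on a late event that the primary test ignores, and step 2 would then no longer hold.
- Population: the analysis plan in Section 10.1 places the primary endpoint at 10 mg/kg, then pools the three participants treated at 15 mg/kg, with a sensitivity analysis that leaves them out.

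**The case against.** A reader might infer that participants entered after the fourth toxicity add nothing. The documents do not support that. Only the reject or not-reject decision is fixed. Section 10.1 also plans proportions with 95% confidence intervals and Kaplan-Meier estimates, Section 10.4 plans trough-level and pharmacodynamic associations that depend on the number enrolled, and Section 10.5 plans quality-of-life analyses. Section 2.5 describes this as the drug's first study in KS. A sponsor could reasonably choose to go on for those reasons, but the protocol does not say so.

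A reader might also infer that accrual runs unwatched. It does not. Beyond the hold, Section 5.1 requires CTEP review before accrual resumes without changes. Section 4.5 requires 24-hour notification and a call on continued enrolment for two named conditions. Section 6.3.3 has unacceptable toxicities reported by the end of the current cycle, and Appendix XIII provides monthly and quarterly reviews and a suspension pathway. The hold also reaches part of the endpoint: Stevens-Johnson syndrome is in none of Tables 6-A to 6-C, so a grade 4 case would be unexpected unless the Investigator's Brochure, which is not available here, lists it. These safeguards supply judgement but no number to judge against.

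Finally, the unacceptable-toxicity definition is narrow, so rates of 30% or 40% may be remote. The nearest figures, in Section 2.3.8, are grade 3/4 hypertension in 3/21 (14%) and 3/19 (16%) at 10 mg/kg weekly. That is twice this trial's dosing frequency, and a broader grade range for that one event. At 15% the mean spared is only 1.8 participants, or 1.2 with the lag. This stands, and it limits the expected benefit. But 30% is the rate at which the plan itself calls the drug unacceptable, and there the saving is material.

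**Conclusion.** The point holds as a cheap improvement. The stated power and level reproduce, so this is not an error in the design calculation; a single-stage trial with event-triggered holds is coherent. What is missing is a rule tied to the toxicity count on which the primary test depends, so accrual may continue after that test is certain to fail. At the plan's unacceptable rate of 30% this would involve on average 7.2 participants (5.5 with an assumed lag of two). At the acceptable 10% it would involve 0.6, so a tolerable drug is hardly affected. The enrolment figures assume a constant toxicity rate, independent participants and, where a lag is shown, a delay that the protocol does not specify. They compare closing at the fourth event with always enrolling 20, so any accrual that the existing hold or reviews would have stopped reduces the saving. The absence of any cost in level or power depends on using one count for both stopping and testing.

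**What to change.** First settle the count. Reconcile the attribution threshold between Sections 10.1 and 10.2, and state whether the three participants treated at 15 mg/kg are included.

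Then add to Section 10.2: *Accrual closes when a fourth participant in the primary analysis population is confirmed by the protocol chair, medical monitor and statistician to have an unacceptable toxicity counted in the primary endpoint (first two cycles, Section 9.0); H0 is then not rejected.*

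In Section 3.3.1, replace the range of 6 to 20 with: *20 participants unless accrual closes under Section 10.2.*

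The cost is a few sentences. The reporting deadline in Section 6.3.3, the monthly calls and the deciding group in Appendix XIII already exist. The real price is precision: if accrual closes early, the response, correlative and quality-of-life estimates rest on fewer participants. The rule governs accrual only and changes no dose or treatment rule for those already enrolled.
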